10.1.2 Assessment of Severity

The medically-qualified Investigator should classify the severity (intensity) of each AE as:

Mild	Awareness of sign or symptom, but easily tolerated
Moderate	Sign or symptom causes discomfort, but does not interfere with normal activities
Severe	Sign or symptom of sufficient intensity to interfere with normal activities

10.1.3 Assessment of Causality

The medically-qualified Investigator must determine the relationship to study treatment for each AE as **Unrelated** or **Related**.

In assessing the causality, the Investigator will take into consideration the known safety profile of NT-814 from prior clinical experience, the findings from non-clinical safety assessments, the temporal relationship with dosing, any effect of de-challenge or re-challenge, the subject's past medical history, the contribution from study procedures or restrictions, and the use, if any, of concomitant medications.

10.1.4 Serious Adverse Event Reporting

Once the Investigator determines that an event meets the protocol definition of an SAE, he/she must report the SAE to the Pharmacovigilance Service Provider, Emas Pharma, immediately (within 24 hours). Any follow-up information on a previously reported SAE will also be reported to Emas within 24 hours.

If the Investigator does not have all information regarding an SAE, he/she will not wait to receive additional information before notifying Emas of the event and completing the appropriate data collection form. The Investigator will always provide a preliminary assessment of causality at the time of the initial report.

Emas Pharma contact details for SAE submission can be found at on the front page of this protocol.

The primary mechanism for reporting SAEs to Emas Pharma will be a paper collection form.

Fax transmission or 'scan & email' of the SAE form is the preferred method to transmit this information to the project contact for SAE receipt. In rare circumstances and in the absence of either email or fax equipment, notification by telephone is acceptable, with a copy of the SAE data collection form sent by overnight mail. Initial notification via the telephone does not replace the need for the Investigator to complete and sign the SAE data collection form within the designated reporting periods

The Investigator must notify his or her IRB of the SAE, as required by local regulatory authorities and in accordance with IRB policy. NeRRre will submit to the regulatory authorities all safety updates and periodic reports, as required by applicable regulatory requirements.

All SUSARs that occur with the IMP within or outside the concerned clinical trial will be reported in compliance with the applicable regulatory authorities and IRBs. Fatal or life-threatening SUSARs must be reported within 7 calendar days and other SUSARs within 15 calendar days.

10.2 Pregnancy

Female subjects will be instructed that they should report to the Investigator if, despite the measures in place to prevent pregnancy, they become pregnant during the study or within 30 days after their last dose of IMP, including any pregnancy occurring during the study but confirmed after completion of the study.

Any female subject reporting a pregnancy during the study will be withdrawn from the study immediately; no further IMP may be administered.

In the event that a subject becomes pregnant during or within 30 days after the end of the study, the Investigator will collect and record information on that pregnancy on the appropriate form and submit it to Emas within 24 hours of learning of a subject's pregnancy through the same process as reporting an SAE. The subject will also be followed to determine the outcome of the pregnancy. Information on the status of the mother and child will be forwarded to the Emas. Generally, follow-up will be no longer than six to eight weeks following the estimated delivery date. Any premature termination of the pregnancy will be reported.

Pregnancy itself is not considered an AE. However, any pregnancy complication, spontaneous or elective abortion for medical reasons, still birth, neonatal death, or congenital anomaly will be recorded as an AE or SAE as applicable.

11 STATISTICAL CONSIDERATIONS

Statistical analysis and reporting will be performed by Quotient.

11.1 Sample Size

In total, up to 42 subjects will be enrolled into the study, 8 per active dose level and 10 on placebo. No formal sample size assessment has been conducted but this sample size is considered sufficient for the objectives of the study to be achieved.

11.2 Analysis Sets

A subject is defined as a volunteer who was allocated a unique screening number. All subjects will be classified as one of the following:

- A screening failure is defined as a subject who signed the informed consent but did not satisfy the relevant inclusion/exclusion criteria prior to Cycle 1.
- An enrolled subject is defined as either:
 - a subject who signed the informed consent, was considered to have satisfied all the relevant inclusion/exclusion criteria prior to Cycle 1, started Cycle 1 (i.e. completed the PD sample procedures on Day 1/2, Cycle 1), was not randomized and did not receive any Investigational Medicinal Product (IMP);
 - or a subject who signed the informed consent, was considered to have met the relevant inclusion criteria prior to and during Cycle 1, was randomized and received at least one dose of IMP.

The following data sets will be used for the statistical analysis.

Enrolled Set: All enrolled subjects as defined above.

Safety Set: All enrolled subjects who received at least one dose of IMP. Subjects will be analyzed according to treatment (dose level) received.

Pharmacodynamic (PD) Set: all subjects in the Safety Set for whom there is adequate Cycle 1 and Cycle 2 PD data to derive the primary endpoints.

Analysis sets will be identified prior to analysis of the study data.

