6 STUDY DESIGN

The study uses a randomized, single-blind, placebo-controlled design. The study will consist of two cohorts, with the second cohort being optional depending on the pharmacodynamic (hormonal) response observed in Cohort 1.

Cohort 1 will consist of 32 subjects randomized to receive NT-814 40mg, 80mg, 120mg or placebo once daily in parallel groups, 8 subjects in each group. After Cohort 1 complete Cycle 2, the pharmacodynamic data will be assessed by a team comprising of the Sponsor medical representative, Sponsor medical expert, Investigator and statistician. If a maximal response (estradiol reduction) is not observed at the lower doses the higher dose of 160 mg dose will be assessed. A maximal response will be considered as having been achieved if the response observed at 120 mg is not meaningfully greater than that observed at 80 mg. In the case that any subjects in Cohort 1 withdraw or are withdrawn from the study prior to completion of Cycle 2 they will be replaced at the discretion of the Sponsor.

If the 160mg dose is to be assessed an additional Cohort 2 will be enrolled – consisting of 10 subjects randomized to receive either NT-814 160mg (8 subjects) or placebo (2 subjects).

Subjects will participate in the study during two consecutive menstrual cycles.

After obtaining written informed consent, each subject will undergo screening procedures within 21 days before the anticipated start of the baseline assessment cycle (Cycle 1).

Eligible subjects will first attend the study unit on the morning of either Day 3 or 4 of Cycle 1 (where Day 1 is the first day of menstruation) for the start of the baseline assessment cycle. Blood samples will be collected for measurement of hormones (estradiol, progesterone, LH, and FSH).

Subjects will return to the study unit for a further three out-patient visits on the mornings of Day 9 or 10, Day 15 or 16, and Day 21 or 22. Blood samples for serum hormones will be collected at each visit. Samples for serum hormone assessment must be taken at the same time of day on all days (± 1 hr).

At the clinic visit on Day 21 or 22, subjects will additionally have safety assessments performed.

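### Section 11.2 defines enrolment by a Cycle 1 Day 1/2 hormone sample that is never taken, leaves randomized-but-undosed women unclassified, and makes the Safety Set conditional on an eligibility judgement

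*Protocol*

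**What the plan says.** Section 11.2 of the protocol starts from every volunteer given a screening number and states: "All subjects will be classified as one of the following". There are two classes.

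- **Screening failure:** a consented woman who "did not satisfy the relevant inclusion/exclusion criteria prior to Cycle 1".
- **Enrolled**, by either of two limbs. Limb (a) is for a woman eligible before Cycle 1 who "started Cycle 1 (i.e. completed the PD sample procedures on Day 1/2, Cycle 1), was not randomized" and received no IMP. Limb (b) is for a consented woman who "was considered to have met the relevant inclusion criteria prior to and during Cycle 1, was randomized and received at least one dose of IMP".

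Two further analysis sets are nested in this definition. The Safety Set is "All enrolled subjects who received at least one dose of IMP". The PD Set is "all subjects in the Safety Set for whom there is adequate Cycle 1 and Cycle 2 PD data to derive the primary endpoints".

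Two other places bear on it. Section 6 says: "Eligible subjects will first attend the study unit on the morning of either Day 3 or 4 of Cycle 1". Section 7 has its own rule, under which a woman is enrolled at her first Cycle 1 assessment, with no condition on randomization or dosing.

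**The concern.** An Enrolled Set should show who entered the trial and what became of them. A safety population should depend on exposure and nothing else. Section 11.2 appears to fail on both counts. Its first limb rests on a sample that is not scheduled, its two limbs leave a gap between randomization and first dose, and its Safety Set carries an eligibility condition.

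Loss between the start of Cycle 1 and dosing is foreseeable in this design. Eligibility is verified again before dosing (Section 7.2), and laboratory values, blood pressure, ECG and drug screen are reassessed late in Cycle 1, some of them again at the start of Cycle 2 (exclusion criteria 6 to 9). Women who leave at that stage are the ones limb (a) was meant to hold. An analysis plan that follows Section 11.2 would inherit the fault.

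**Working it through.** **Step 1. Is there a Cycle 1 Day 1/2 hormone sample?** Table 9-1 schedules hormone samples on Days 3/4, 9/10, 15/16 and 21/22 of each cycle. Day 1 of Cycle 1 marks only the start of menstrual flow and has no clinic visit. The count is 4 + 4 = 8 samples per woman. Table 9-3 budgets 8, so the protocol's own figure is reproduced and there is no room for a ninth. Limb (a) cannot be met by anyone.

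**Step 2. What is left of the Enrolled Set?** With limb (a) empty, only limb (b) remains, and it requires a dose. Read literally, the Enrolled Set and the Safety Set contain the same women, so the Enrolled Set adds nothing to the account of who entered the trial.

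**Step 3. Is the classification exhaustive?** Six possible histories were taken through the definitions, first as written and then with Day 1/2 replaced by the scheduled Day 3/4.

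| History | As written | Day corrected only |
|---|---|---|
| 1. Fails the criteria before Cycle 1 | Screening failure | Screening failure |
| 2. Eligible, leaves before Cycle 1 | None | None |
| 3. Starts Cycle 1, not randomized | None | Enrolled, limb (a) |
| 4. Randomized, not dosed | None | None |
| 5. Randomized and dosed, considered to meet the inclusion criteria | Enrolled, limb (b) | Enrolled, limb (b) |
| 6. Randomized and dosed, considered not to meet an inclusion criterion | None | None |

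Unclassified: 4 of 6 as written, 3 of 6 after the day is corrected. These are types of history, not expected frequencies. History 4 fails limb (a) because she was randomized and limb (b) because she was not dosed. Correcting the day does not help her.

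**Step 4. Does the Safety Set depend on eligibility?** A dosed woman can be enrolled only through limb (b), which requires that she "was considered to have met the relevant inclusion criteria prior to and during Cycle 1". History 6 is therefore exposed but outside the Safety Set and, by nesting, outside the PD Set.

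**Step 5. Size if that happens.** Section 11.1 plans 8 women per active dose and 10 on placebo, which gives 4 × 8 + 10 = 42, as stated. One excluded woman is 1/8 = 12.5% of an active arm or 1/10 = 10% of the pooled placebo group. This is the cost per case and says nothing about how likely a case is.

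**The case against.** The strongest defence is that Day 1/2 is a label slip. Limb (a) itself speaks of having started Cycle 1, and Section 7 gives a usable rule. The women concerned would not vanish from the record either. Section 7 keeps screening and enrolment logs, Section 7.4 records each consented woman's early discontinuation with its reason, and Section 11.3 lists all data. A reader might infer that pre-dose losses go unreported altogether; these provisions do not support that. What stands is that the set definition gives the wrong count and conflicts with Section 7.

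On the undosed gap, Section 6 places randomization and first dose at the same visit, so cases should be few. Such a woman would be outside the Safety and PD Sets under any sensible definition. Only disposition is affected.

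On the Safety Set, limb (b) turns on what was considered at the time, so a violation found later removes nobody. Sections 7.2 and 8.3 allow only women who still meet the criteria to be randomized and dosed. Limb (b) also names inclusion criteria only, whereas the timed laboratory, blood pressure, ECG and drug-screen rules are exclusion criteria. Inclusion criterion 5, good health judged partly on laboratory findings, vital signs and ECG, could still bring such a result in. The condition should rarely bite, but it has no place in a safety population.

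Two stronger readings are tempting. Because only the subject is blinded, a reader might infer that staff could remove women from the sets once the arm is known. The text does not support this: limb (b) dates its judgement to before and during Cycle 1, randomization comes in Cycle 2, and the sets are to be identified before analysis. A reader might also apply an assumed loss rate to the planned 42 to count the missing women. The protocol gives no such rate, and the synopsis describes the 42 as completed subjects, so pre-dose losses would come from a larger and unstated number of Cycle 1 starters.

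**Conclusion.** The point holds as a fault in the definitions, with limited consequences. Three things are stated wrongly in Section 11.2: the sampling day in limb (a), which empties that limb and conflicts with Section 7; the gap for randomized-but-undosed women in a classification meant to be exhaustive; and an eligibility condition passed on to the Safety and PD Sets.

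The first two affect only the Enrolled Set and disposition counts. The third could remove an exposed woman, but only if she was dosed while considered not to meet an inclusion criterion, which the pre-dose checks are there to prevent. No bias from knowledge of the arm is shown, and no hormone or safety estimate is shown to change.

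The conclusion assumes the definitions are applied as worded. If the day is silently read as 3/4, the first fault disappears and the other two remain. It is worth correcting because the change is trivial and the analysis plan will build on these sets.

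**What to change.** Rewrite Section 11.2 and carry the wording into the Reporting and Analysis Plan:

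- **Enrolled Set:** all women who completed the first Cycle 1 assessment on Day 3/4, whatever happened later, in line with Section 7.
- **Disposition:** count all randomized women, dosed or not.
- **Safety Set:** all women who received at least one dose of IMP, analysed by treatment received, with no reference to eligibility.
- **PD Set:** keep as a subset of that Safety Set.

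This places histories 3 to 6. History 2, an eligible woman who leaves before Cycle 1, still needs a class of her own, or the claim to classify every subject should be dropped.

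The cost is a few lines of text, with no new data, visits or samples and no change to the planned numbers.

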11.3 Data Analysis and Reporting

Full details of the proposed statistical and pharmacodynamic analyses will be documented in the Reporting and Analysis Plan (RAP), which will be written following finalization of the protocol and finalized before locking the database.

Where applicable, values will be converted from local to Système International (SI) units for reporting; both original and converted values will be listed.

PD and safety data will be presented by means of descriptive statistics and figures, as appropriate, by treatment arm and time point. All data will be listed.

Summary statistics will be based primarily on non-missing values. Full details on the handling of missing values will be defined in the RAP.

11.3.1 Baseline assessment

Descriptive statistics will be performed on relevant screening and baseline data (i.e. data collected prior to the treatment administration) and on demographic characteristics for each treatment group.

In general, baseline for safety assessments will be the last value recorded before the first dose of IMP. Baseline for PD assessments will be the time-matched value from Cycle 1.

11.3.2 Safety analysis methodology

The safety and tolerability profile will be assessed versus baseline conditions, and descriptive statistics for change from baseline will be produced, where applicable.

A treatment-emergent analysis will be done for AEs. AEs will be tabulated by Medical Dictionary for Regulatory Activities (MedDRA) preferred term and system organ class. Tabulations by severity and drug-relatedness will also be made.

Safety data will be summarized by dose of NT-814 including placebo.

11.3.3 Pharmacodynamic analysis methodology

The pharmacodynamic data (i.e. LH, FSH, estradiol and progesterone) in Cycle 2 will be assessed versus baseline (Cycle 1), and descriptive statistics for change from baseline will be produced, where applicable.

The changes from baseline will be analyzed using a fixed effects model with treatment as a fixed effect and the corresponding baseline value as a covariate. The adjusted arithmetic means from the model for the changes from baseline including 95% confidence interval (CI) will be presented for each treatment. In addition, the following comparisons will be performed and the difference in the adjusted arithmetic means and 90% CI will be presented:

- each dose level of NT-814 vs placebo

This analysis will be performed for each day separately (i.e. Days 3/4, 9/10, 15/16 and 21/22). A repeated measures analysis may be used if considered appropriate.

For the exploratory analysis of the change in menstrual cycle length, the length of Cycle 2 will be assessed versus baseline (length of Cycle 1), and descriptive statistics for change from baseline will be produced, where applicable.

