5 STUDY OBJECTIVES AND CORRESPONDING ENDPOINTS

The study objectives and corresponding endpoints/study outcomes are presented in [Table 5-1](#).

Table 5-1 Objectives and Corresponding Endpoints/Study Outcomes

Objectives	Endpoints/Study Outcomes
Primary	
To determine the effects of NT-814 given at doses of 40 mg, 80 mg, 120 mg, and 160 mg once daily for approximately 21 days on GnRH pathway hormones in healthy female subjects	
 • Change from baseline in serum LH, FSH, estradiol and progesterone over a full menstrual cycle
Secondary	
To evaluate the safety of NT-814	
 • 12-lead ECGs: abnormalities; change from baseline in quantitative parameters (RR interval, PR interval, QRS duration, absolute QT interval and QTcF) • Change from baseline in clinical laboratory assessments (hematology, biochemistry) • Change from baseline in vital signs (BP, pulse rate, weight) • Nature and severity of TEAE; withdrawals due to TEAE
Exploratory	
To evaluate the pharmacokinetic-pharmacodynamic (PK-PD) relationship of NT-814	
 • NT-814 plasma concentration levels concurrent with serum LH, FSH, estradiol and progesterone during Cycle 2
To evaluate the effect of NT-814 on menstrual cycle length	
 • Change from baseline (Cycle 1) in the length of the menstrual cycle

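### Cycle length gets only descriptive change from Cycle 1, with no planned dose-versus-placebo estimate and no adjustment for Cycle 1 length, although the same section gives the hormones both

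*Protocol*

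**What the plan says.** Protocol Section 5, Table 5-1, lists an exploratory objective, "To evaluate the effect of NT-814 on menstrual cycle length", with the endpoint "Change from baseline (Cycle 1) in the length of the menstrual cycle".

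Section 11.3.3 gives the matching analysis: "For the exploratory analysis of the change in menstrual cycle length", the text continues, "the length of Cycle 2 will be assessed versus baseline (length of Cycle 1), and descriptive statistics for change from baseline will be produced". It names no model, contrast or interval.

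For LH, FSH, estradiol and progesterone the same section specifies a "fixed effects model with treatment as a fixed effect and the corresponding baseline value as a covariate", adjusted means with 95% CI, and differences with 90% CI for "each dose level of NT-814 vs placebo". That model is tied to the hormone sampling days: "This analysis will be performed for each day separately (i.e. Days 3/4, 9/10, 15/16 and 21/22". It therefore cannot be read as covering cycle length, which has one value per cycle.

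Section 11.3 says that PD data are summarized by treatment arm and leaves full details of the proposed analyses to the Reporting and Analysis Plan (RAP). Section 11.1 gives 8 subjects per active dose and 10 on placebo, and states that no formal sample size assessment was made.

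**The concern.** The objective is a treatment effect in a randomized, placebo-controlled trial, but the stated analysis compares each subject only with herself. A change within one arm mixes any drug effect with ordinary cycle-to-cycle variation. The placebo arm is there to separate the two, and no comparison with it is planned for this endpoint.

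Cycle 1 length is the baseline value of this endpoint and is already collected, yet it serves only as the number subtracted. Unless the two cycle lengths are very highly correlated, subtracting the whole baseline adds noise that a covariate would remove. With 8 per arm, a chance difference in mean Cycle 1 length passes partly into the difference in change.

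The endpoint has some weight. Section 4.1 cites a 21-day study of another NK3 antagonist in regularly cycling women that found delayed ovulation and a longer cycle. A shift in cycle timing also bears on how hormone values at fixed cycle days are read.

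**Working it through.** **Figure to reproduce.** The protocol gives no SD, correlation, effect size or power for cycle length, so there is none. Its head-count is consistent: 4 × 8 = 32 in Cohort 1; 32 + 10 = 42 with Cohort 2; placebo 8 + 2 = 10.

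**Inputs from the protocol.** Arms of 8 and 8 (Cohort 1) or 8 and 10 (both cohorts); 90% CI for differences, as for the hormones.

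**Assumptions, not in the protocol.** Correlation ρ between Cycle 1 and Cycle 2 length of 0.3 to 0.9; between-woman SD σ of 3 days (range 2 to 4), equal in both cycles; every cycle length observed.

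**Step 1: is the unadjusted difference biased?** No. Four arms of 8 were simulated with a true effect of 4 days, 10,000 runs per ρ. The mean estimate was 3.99 to 4.00 days from change scores and 4.00 to 4.01 from the adjusted model.

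**Step 2: variance of a dose-minus-placebo difference.**
- Change score: 2σ²(1 − ρ)(1/n₁ + 1/n₀)
- Adjusted for Cycle 1 length: σ²(1 − ρ²)(1/n₁ + 1/n₀)
- Ratio, adjusted to change score: (1 − ρ²) / [2(1 − ρ)] = (1 + ρ)/2

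The ratio does not depend on σ. It is a large-sample value, so the simulated ratio with 8 per arm is shown beside it.

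**Step 3: 90% CI half-width, 8 versus 8.** The error is pooled over 32 subjects. Residual df are 32 − 4 = 28 unadjusted and 27 adjusted. The adjusted variance is multiplied by 1 + 1/(27 − 1) to allow for baseline imbalance in small samples.

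At ρ = 0.5, σ = 3:
- Change score: SD = 3√(2 × 0.5) = 3.00; half-width = 1.701 × 3.00 × √(2/8) = 2.55 days
- Adjusted: SD = 3√(1 − 0.25) = 2.60; half-width = 1.703 × 2.60 × √(2/8) × √(1 + 1/26) = 2.25 days

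| ρ | Ratio, large sample | Ratio, simulated | Variance cut, simulated | Half-width, change score (days) | Half-width, adjusted (days) |
|---|---|---|---|---|---|
| 0.3 | 0.65 | 0.67 | 33% | 3.02 | 2.48 |
| 0.5 | 0.75 | 0.78 | 22% | 2.55 | 2.25 |
| 0.7 | 0.85 | 0.88 | 12% | 1.98 | 1.86 |
| 0.9 | 0.95 | 1.00 | 0% | 1.14 | 1.13 |

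Half-widths scale with σ. At ρ = 0.5 they go from 1.70 to 1.50 days for σ = 2, and from 3.40 to 3.01 for σ = 4. With 8 versus 10 and 42 subjects, at ρ = 0.5 and σ = 3, the change is from 2.40 to 2.11 days.

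**Step 4: chance imbalance.** The difference in mean Cycle 1 length between two arms of 8 has SD 3 × √(2/8) = 1.5 days. An imbalance of that size moves the unadjusted difference by (1 − ρ) × 1.5 = 0.75 day at ρ = 0.5. This is part of the sampling variance in Step 2, not an addition to it.

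**The case against.** A reader might infer that the trial cannot estimate the drug effect on cycle length at all. The documents do not support that. Section 11.3 presents PD data by treatment arm, so the placebo summary stands beside each dose. From n, mean and SD per arm, anyone can form an unbiased difference and an interval.

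A reader might also infer that regression to the mean biases the arm means. It acts on individual women. Eligibility is first judged at screening, before Cycle 1, on having regular, approximately monthly periods; subjects are not selected on Cycle 1 length, and randomization follows at the start of Cycle 2. Only chance imbalance remains, and at 0.75 day it lies well inside the 2.55-day half-width.

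It can fairly be said that the endpoint is exploratory and absent from the synopsis, that no power is claimed, and that the RAP may add a model. The first two limit the weight of the point. The third does not remove it: Section 11.3 defers details of the proposed analyses, and the analysis proposed for cycle length is stated and is the weaker one. A RAP that followed the protocol could stop there.

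The size of the gain rests on an undocumented correlation and vanishes near 0.9; that stands. So does the limit set by ascertainment. Section 6 obtains the start of the next cycle by asking at the follow-up visit two weeks after the last dose, which Table 9-1 places on Days 35-38. A cycle still running then has no recorded end. This affects descriptive and adjusted analyses alike and is a separate matter, but the model does not cure it.

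**Conclusion.** The point holds as a minor improvement to an exploratory analysis. Section 11.3.3 plans neither a placebo-controlled estimate of the cycle-length effect nor an adjustment for Cycle 1 length, while the stated objective is the effect of NT-814 and the same section already contains the right model. The missing contrast and interval stand at any correlation. The precision loss is about a third of the variance at ρ = 0.3, about a fifth at 0.5, about an eighth at 0.7 and nothing at 0.9. These figures assume equal SDs in the two cycles and fully observed lengths; the half-widths in days also assume an SD of 3 days.

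**What to change.** In Section 11.3.3, keep the descriptive statistics for cycle length and add: *Change in cycle length will also be analyzed with treatment as a fixed effect and Cycle 1 length as a covariate. Adjusted means with 95% CI and the difference of each NT-814 dose from placebo with 90% CI will be presented as exploratory results. The number of subjects whose Cycle 2 length was not observed by the follow-up visit will be reported for each arm.*

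The cost is one residual degree of freedom (28 to 27 in Cohort 1) and one extra table. No further subjects, visits or data are needed. The count of unobserved lengths does not resolve those cycles; it shows how far the estimate can be trusted.
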